Study Co-ordinator	[name] Advanced Neonatal Nurse Practitioner St Michael's Hospital University Hospitals Bristol NHS Trust [name]
	Email: [contact]
Sponsor	University Hospitals Bristol NHS Foundation Trust
	Research & Innovation
	Level 3, Education and Research Centre
	[name]
	Bristol BS2 8AETel: [name]
	Email: R&[contact]
Joint-sponsor(s)/co-	NA
sponsor(s)	
Funder(s)	NIHR RfPB
Key Protocol Contributors	[name] FRPCH MD Consultant Senior Lecturer Neonatal Medicine Level D St Michael's Hospital, [name]. [contact] Email: [contact]

	[name] Senior Research Fellow Centre for Academic Child Health, University of Bristol Bristol Medical School, [name] [contact] Email: [contact]
	[name] Advanced neonatal nurse practitioner St Michael's Hospital University Hospitals Bristol NHS Trust [name] Email: [contact]
Committees	Study steering group [name] (Chair of the steering group) Level D, St Michael's Hospital [name] Email: [contact]

FUNDING AND SUPPORT IN KIND

FUNDER(S)	FINANCIAL AND NON FINANCIALSUPPORT
(Names and contact details of ALL organisations providing funding and/or support in kind for this study)	GIVEN
NIHR RfPB	£148,412.00

STUDY SUMMARY

Study Title	"CoolCuddle" study: Development and evaluation of a
	standard procedure of a cuddling process allowing
	parents to cuddle their babies undergoing cooling
	therapy.
Internal ref. no. (or short title)	CoolCuddle
Study Design	Cohort Study
Study Participants	Infants undergoing therapeutic hypothermia who are admitted
	to the NICU at St Michael's Hospital or at Southmead
	Hospital in Bristol and their parents
	Neonatal staff involved in the "CoolCuddle" process
Planned Size of Sample (if applicable)	Stage 1: 4-6 cooled parent/s-infant pairs over 3 months
	Stage 2: 20-24 cooled parent/s-infant pairs over 12 months
Follow up duration (if applicable)	
Planned Study Period	1 st Sept 2019 to 1 st April 2021
Research Aim	To incorporate a refined "CoolCuddle" protocol into the
	existing cooling therapy pathway that will allow parents to
	cuddle their babies during cooling therapy.
Objectives	To develop the existing cuddling technique for non-cooled
	babies receiving intensive care into a "CoolCuddle" protocol
	using the physiology stability data during cuddling and
	qualitative data from nurses, parents and medical staff by
	adopting "talk aloud " technique.
	To investigate whether the "CoolCuddle" protocol would
	maintain stable cooling therapy, respiratory, cardiovascular
	and neurophysiology.

	To develop a modified cooling therapy pathway with the
	"CoolCuddle" protocol incorporated into the pathway.
Outcomes	Refined "CoolCuddle" protocol at the end of phase 1.
	Physiological stability as measured by means and variability
	of surface and core temperature, ventilation, cardiovascular
	and neurophysiology parameters between the epochs of pre,
	during and post "CoolCuddle".
	Modified cooling therapy pathway with "CoolCuddle" protocol
	integrated within the pathway.
	Maternal mood, mother-infant bonding, father-infant
	attachment, mode of feeding at discharge and length of stay
	at hospital.
	Qualitative feedback on the "CoolCuddle" technique from
	parents and neonatal staff to refine the pathway and facilitate
	rollout into practice.
	Incidence and detailed description of any adverse events

ROLE OF STUDY SPONSOR AND FUNDER

University Hospitals Bristol NHS Foundation Trust are the sponsor for this study and overall responsibility for the initiation and management of the research.

National Institute for Health Research under its Research for Patient Benefit programme (RfPB) funds this study. The sponsor or the funder does not influence the study design, conduct, data analysis and interpretation, manuscript writing, and dissemination of results. The chief investigator will send a draft copy of any proposed publication, articles, presentations and press releases to the RfPB at the same time as submission for publication or at least 28 days before the date intended for publication whichever is earlier.

ROLES AND RESPONSIBILITIES OF STUDY MANAGEMENT COMMITEES/GROUPS & INDIVIDUALS

Study management group

The study management group will comprise [name], [name], [name] and [name] and will meet every 4-6 weeks to discuss the progress of the study and deal with issues arising from the study to enable achieving the deadlines.

Study steering group

The study steering group is chaired by [name], Emeritus Professor of Neonatology. Other members of the steering group include an independent statistician and neonatologist from another Trust. The steering committee is independent of the sponsor and the funder and will meet soon after study initiation to agree on the terms of reference of the group. They will meet four times during the study. The committee will monitor the study progress, advise on its further progression, and review adverse events.

Periodic reports of all adverse events, and other events of interest (detailed in Section 8.6) will be sent to the study steering group for review.

The Committee will make a recommendation to the study management group about continuation of the study. The study may be terminated early on the instruction of the study steering group and with agreement by sponsor. Study steering group meeting minutes will be provided to the sponsor.

Parent advisory group:

- Physiology data every 5 min; continuous adverse events monitoring

Post-cuddle 30-60 mins

Data collection: Physiology data every 5 mins continuous adverse events monitoring

Data at Day 5-7 of life of baby

- Mode & type of feeding; length of hospital stay
- Mothers: Edinburgh Postnatal Depression scale (EPDS)¹ Mother-to- infant bonding scale (MIBS)³

Data at 8 weeks of life of baby

- Mothers: Edinburgh Postnatal Depression scale
 Mother-to-infant bonding scale
 - Fathers: paternal postnatal attachment scale²

Outcome

- Optimise data collection for physiological variables and adverse events
- Refined "CoolCuddle" protocol for testing in the stage 2

Stage 2 (Main dataset)

Data

Every cuddle episode:

- *Physiology:* Ventilation, oxygenation, heart rate, blood pressure, aEEG, temperature, NIRS (if available)
- Adverse events: dislodgement of tubes/catheters, escalation of intensive care etc..

NICU stay:

Qualitative: opinions of staff (n=6) about "CoolCuddle" in focus group meeting

Before discharge:

- Mode of feeding, length of hospital stay
- Mother: EPDS¹, MIBS² at 5-7 day of life of baby

When baby is 8 weeks old:

- Mother: EPDS¹, MIBS³.Father: paternal postnatal attachment scale²
- Qualitative: opinion of parents regarding the CoolCuddle

Entire duration of study

Outcomes

- Difference in the distribution, mean/ median and variability of ventilatory, cardiovascular, temperature and neurophysiology between the pre-cuddle, CoolCuddle and post-cuddle
- Mode of feeding compared to existing audit data
- Parent-infant bonding scores compared to normative data
- Qualitative feedback on the "CoolCuddle" protocol
- Rate and type of adverse events

Stage 3 (Report and dissemination)

Final data analyses

- NIHR report
- Manuscript preparation, submission to journal
- Dissemination: presentation, publication, Bliss and parent advisory group involvement, southwest
- neonatal network
- "CoolCuddle" protocol + data collection tool of adverse events and bonding scores for roll out or further study

CoolCuddle study protocol

STUDY PROTOCOL

"CoolCuddle" study: Development and evaluation of a standard procedure of cuddling process allowing parents cuddle their babies undergoing cooling therapy.

1 BACKGROUND

In the NHS, each year around 2100 infants (3/1000 live births) undergo cooling therapy to reduce brain injury following exposure to lack of oxygen and blood supply to the whole body around the time of birth⁴. This condition is called hypoxic-ischemic encephalopathy (HIE) and cooling therapy is the current standard treatment⁵ for infants with HIE. The cooling therapy involves cooling the whole body with a blanket or wrap that contains cold or warm water circulating through it and covering the baby's body. During cooling therapy, body temperature is maintained at 33-34°C for three days followed by 6-8 hours of rewarming to normal temperature of 36.5°C⁶. Most of the cooled infants often need intensive care including support for breathing, heart function and monitoring of brain activity including identifying and treating seizures⁶. As cooling therapy needs to be delivered in tertiary neonatal intensive care units (NICUs)⁵, babies with HIE born in peripheral hospitals will be transferred to tertiary NICU soon after birth and mothers who will be recovering from the delivery typically arrive a day later to the tertiary NICU. On arrival, parents often receive the news that their baby may die or suffer brain damage⁷. Furthermore, our national survey of neonatal intensive care units (NICU) offering cooling therapy showed that 95% of units do not allow parents to cuddle their babies during the entire cooling therapy period due to concerns of destabilising the cooling process and intensive care⁸. This practice has been reported to compromise parent-infant bonding by 80% of mothers in a recent cross-sectional survey⁹. The physical separation ensuing from transferring the baby to a distant NICU offering cooling therapy and the lack of emotional support after receiving the news that their baby may die or suffer brain damage further impedes the development of parent-infant bonding¹⁰. Impaired parent-infant bonding affects the establishment of breastfeeding¹¹, leads to emotional neglect in the newborn period¹², influences the emotional and cognitive development of children¹³, and results in postnatal stress or depression in parents^{14,15}, which if persistent may lead to behavioural problems in childhood^{16,17}. Given that the survivors of cooling therapy are already at a higher risk of neurodevelopmental disability with 22% having disability at 18 months¹⁸, and 18-20% having cerebral palsy^{19,20}and 30-40% having intellectual disabilities at school-age^{21,22}, compromised parent-infant bonding might contribute to or worsen the outcome in these vulnerable infants.

To promote parent-infant bonding for preterm infants in the neonatal intensive care unit (NICU), it is standard practice to encourage family-centred care and cuddling of babies undergoing intensive care²³. A recent small feasibility study from the United States showed that cuddling stable cooled

babies not needing intensive care did not affect cooling therapy and was favoured by parents and nurses²⁴. However, the majority of cooled babies in the UK (approximately 80%) receive intensive care, including breathing support with mechanical ventilation and are cooled using a different servocontrol machine compared to the US units (Criticool vs Blanketrol)²⁵. It is not yet known whether adopting the standard NICU practice of cuddling babies during intensive care for cooling babies will affect the cooling process and the intensive care. Therefore in this study, we will refine the usual technique of parents cuddling babies receiving intensive care and develop a "CoolCuddle" protocol (stage 1) and adapt it to babies receiving cooling therapy after evaluating the safety to babies and the impact on parents and health care staff (stage 2). This research involves the nursing care of the babies undergoing cooling therapy addressing the ongoing uncertainty about parents cuddling babies during cooling therapy and could potentially improve parent-infant bonding with a long-term effect on the mental wellbeing of parents and cognitive development of children.

2 RATIONALE

The study will initially refine the cuddling technique that is part of the standard care for non-cooled babies receiving intensive care and develop a cuddling protocol ("CoolCuddle") for cooled babies with input from parents and neonatal staff. Subsequently we will test the "CoolCuddle" protocol for 1] its ability to offer physiological stability; 2] potential adverse effects during CoolCuddle; 3] views of parents and neonatal staff about the "CoolCuddle",4] impact of CoolCuddle on mother's mood, bonding with their babies and father's attachment with their babies. Lastly the study will aim to incorporate the "CoolCuddle" protocol in the cooling therapy pathway along with outcomes to be measured including the adverse outcome, maternal mood and parental bonding.

Impaired parent-infant bonding could affect the mental health of parents influencing the emotional and cognitive development of cooled children who are already at higher risk of cerebral palsy and cognitive impairments. The additional lifetime health and social care costs for a child with cerebral palsy are about £750,000; costing the UK economy £650million per year²⁶. The direct costs of cognitive disabilities in Europe are estimated at €43.3 billion accruing from health and mental health services utilisation²⁷ while lifelong welfare support and lost earnings costs additional impacts²⁸. Indeed, HIE is the 12th most prominent contributor to the global burden of disease or disability-adjusted life years and ranks second in the group of neonatal disorders²⁹. Furthermore, postnatal depression needs input from psychological, social and health services costing £8.1 billion per year³⁰. The benefits of improved parental bonding have been widely studied in the preterm infant population, where skin-to-skin and early attempts at supporting parental interaction have been shown to improve breastfeeding rates^{31,32}. Other studies suggest that in term infants NICU admission can also disrupt

the bonding process³³. Due to the high risk of long-term adverse consequences following HIE, even small improvements in outcomes would yield substantial health benefits for individuals and economic benefits for health care services. The anticipated output of this study is a refined "CoolCuddle" protocol that does not affect the cooling therapy or intensive care, and which may enhance parental infant bonding for cooled infants. Better parent-infant bonding may improve the cognitive function of cooled infants and is likely to improve the mental health of parents, reducing the costs to educational, health and social care services.

We have developed this research question through discussions with parents who have had babies with HIE and underwent cooling therapy. They all agreed that evaluating the cuddling of babies during cooling is a very important and relevant question. They all said that they would have loved to do it, had they been offered. Half of fathers interviewed said that they would have liked to cuddle their babies during cooling. All the mothers and the remaining 50% of fathers interviewed wanted to ensure that the cuddling will be safe for the babies, which informed the outcome we wanted to study. Bliss has informed us that this piece of work will provide an important insight into giving babies a better start in life.

3 THEORETICAL FRAMEWORK

There is an urgent need to improve the parent-infant bonding in parents whose babies are cooled for HIE. One of the interventions, which has been shown to promote parent-infant bonding in preterm infants is early parent infant interaction in the form of cuddling. To address the concerns of the impact of cuddling babies during cooling on the effectiveness of cooling therapy, support for breathing and heart function, and brain activity monitoring, we will undertake this study in three stages. In stage 1, we will refine the standard cuddling protocol used in non-cooled babies receiving intensive care using a robust methodology called "talk aloud". In this methodology, nurses involved in moving the baby undergoing cooling from the open incubator to the parents, researchers overseeing the process and the parents will openly and consciously talk about what is happening and how they are feeling during the process. This will involve giving a verbal commentary of their actions during the cuddle process and vocalising the changes they are doing to the standard cuddle. These vocal thoughts will be captured by an audio recorder and a researcher will also make field notes of the process. The research group will meet soon after the cuddle to reflect on the process and use the information collected to refine the cuddling protocol in an iterative process after each cuddle. This stage will involve 4-6 parents-infant pairs in the two sites between September 2019 to January 2020.

In stage 2, we will test the impact of the "CoolCuddle" protocol on the stability of cooling process, intensive care support including support for breathing, heart function and brain activity monitoring, and whether there are any adverse effects. This will be undertaken in 20-24 parents - infant pairs over a period of 12 months. Each infant will have a minimum of one cuddle with their parents. We will compare the physiology data between the pre, during and post cuddle to assess the short-term safety of cuddling babies during cooling. These data will tackle the concerns of the neonatal community regarding the short-term safety of cuddling the babies during cooling by reporting any safety issues including any adverse or serious adverse events. To address the issue of long-term impact of cuddling the babies undergoing cooling therapy, as parent-infant bonding has been shown to be improved with early parent-infant interaction in non-cooled babies, we will measure the maternal mood and parent-infant bonding using validated questionnaires around discharge and when the baby is 8 weeks of age.

Given that the early parent infant interaction including cuddling is the standard care for babies receiving intensive care in the NICU, we will adopt a traffic light system in stage 3 to progress with the findings of stage 2.

Green zone: If there are no adverse effects with the "CoolCuddle" protocol, we will integrate the "CoolCuddle" protocol into the existing cooling therapy pathway at the study centres. The modified "CoolCuddle" protocol including the steps of the "CoolCuddle" process and a data collection tool comprising adverse events and bonding questionnaires will be published on the southwest neonatal network website. We will consider appropriate further methods of investigation to confirm the short and long-term safety in larger sample sizes or rolling out the "CoolCuddle" study to other networks with collection of safety data and bonding scores with further potential funding.

Orange zone: If modifiable adverse events or adverse physiological changes or resolvable issues from parents or healthcare staff persist at the end of the study, we will modify the "CoolCuddle" protocol taking these issues into account. We will explore if there is a specific subgroup of cooled infants where the "CoolCuddle" might not be suitable . We will discuss with the steering committee whether further funding is needed to test the protocol or whether we can proceed as outlined in the green zone.

Red zone: If there are unmodifiable adverse effects at the end of the research, we will abandon the implementation and publish our findings.

During stage 3, we will complete the NIHR report, prepare the manuscript for publication and disseminate the findings.

4 RESEARCH QUESTION/AIM(S)

The overarching aim of the study is to incorporate a robust "CoolCuddle" protocol into the existing cooling therapy pathway.

4.1 Objectives

- 1 To refine the existing cuddling technique practised in neonatal intensive care and develop a "CoolCuddle" protocol using an iterative process employing 'talk-aloud' qualitative methods with parents, neonatal nurses and neonatologists and quantitative temperature and physiology data (Stage 1).
- 2 To investigate the safety and effect of the "CoolCuddle" protocol on the temperature, respiratory, cardiovascular and amplitude integrated electroencephalogram (aEEG) during the "CoolCuddle" episodes and qualitative interviews to explore parents' and healthcare staff's opinions (Stage 2).
- 3 To produce a modified "Coolcuddle" protocol with a data collection tool that can be incorporated into the existing cooling therapy pathway (Stage 3).

4.2 Outcomes

- Difference in mean/median and variability of surface and core temperature, ventilation, cardiovascular and neurophysiology parameters between the pre-cuddle, "CoolCuddle" and post cuddle epochs.
 - Day of life when oral feeds established
 - Mode and type of feeding at discharge and 8 weeks
 - Maternal mood assessed using Edinburgh postnatal depression scale¹ when the baby is 5-7 days of age and at 8 weeks.
 - Maternal-infant bonding assessed using Mother-infant bonding score³ when the baby is 5-7 days of age and at 8 weeks.
 - Father-infant attachment assessed using paternal postnatal attachment scale² at 8 weeks
 - Qualitative feedback on the "CoolCuddle" protocol
 - Incidence of adverse events including frequency of administering stop rules for "CoolCuddle", and dislodgement of endotracheal tube, central or peripheral arterial catheter, central venous catheter

5.STUDY DESIGN, METHODS OF DATA COLLECTION AND DATA ANALYSIS

This study will be a cohort study involving a controlled trial without randomisation design recruiting the cooled infants admitted to the NICUs of St Michael's and Southmead Hospital and their parents between September 2019 and January 2021.

5.1 Stage 1: Developing "CoolCuddle" protocol by refining existing cuddling technique using an iterative process (3 months)

Over 3 months, we will use the current family centred cuddling technique that we use for non-cooled babies receiving intensive care for babies receiving cooling treatment on 4-6 parents-infant pairs. We will attempt a minimum of one cuddle session per family up to 2 hours in length. We will refine the protocol by using 'talk-aloud' qualitative methods during each of the "CoolCuddle" sessions. Talk-aloud methods are used to gather data on usability and development of products and tasks³⁴. Talk-aloud methods involve participants describing their actions and how they go about completing the task. The audio-recordings made are used to improve the process through insights and modifications that arise during the session. A member of the research team will also observe all the "CoolCuddle" sessions and make field notes of changes made and actions taken.

We will explore the optimum time and duration to compare physiological data from our pre-set 30-60 minutes epochs before and after the parents cuddle their baby. Using an iterative process, we will refine the cuddling technique throughout stage 1 into a "CoolCuddle" protocol. We have modified our current cuddling technique for the study based on advice from NICU nurses who have expertise in transporting sick newborn infants in ambulances and developmental care specialists. We have undertaken three mock "CoolCuddle" processes in a simulation session to further modify the technique (one of them shown in fig 2). One to two nurses will co-ordinate the cuddling technique. A research nurse will oversee the procedure including collecting the data. A member of the research team will be overseeing the process making field notes.

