- Any instances of the following during the cuddling procedure:
 - o Accidental extubation
 - o Dislodgement of vascular catheters
 - Dislodgement of aEEG electrodes
 - o Needle-stick injury from aEEG electrodes

Data at discharge

.

We will collect data on mode and type of feeding. We will give mothers a mother-infant bonding (MIB) questionnaire and Edinburgh postnatal depression scale (EPDS) to complete around day 5-7 and at 8 weeks. We will collect father-infant attachment scores using a paternal postnatal attachment scale.

Data analysis

We will use the audio recordings of the talk aloud after each CoolCuddle episode to modify the CoolCuddle protocol. After the completion of "CoolCuddle" for each parent-infant pair, key investigators will use the talk aloud audio recordings and field notes made by the researchers to decide on the potential changes to the "CoolCuddle" protocol. We will aim to carry out the talk aloud

process with 4-6 parents-infant pairs. At the end of 3 months, a refined "CoolCuddle" protocol will be produced with involvement from the parent advisory group.

Stage 2: Effect of "CoolCuddle" protocol on the stability of cooling process and intensive care, and parents and healthcare staff opinion. (12 months)

We will use the refined "CoolCuddle" protocol and process on 20-24 cooled infant-parents pairs. The study participants will be recruited as for stage 1. Both parents will be invited for the cuddle. The intervention will be administered by nurses overseen by a research nurse.

All parents will be invited to be interviewed by the qualitative researcher and all who agree will be interviewed at an agreed convenient location or by phone/Skype. These interviews, with up to 20 parents, will explore their views on the refined CoolCuddle protocol and how best to roll it out to other NICUs. Interviews will take place after the 8 weeks questionnaires are collected and will mostly be by telephone so verbal consent will be recorded before each interview takes place. Parents will be sent an interview information sheet and consent form in advance of the interview date.

Staff involved in delivering the CoolCuddle protocol (6 nurses or doctors) at each site (St Michael's NICU and Southmead NICU) will also be invited to participate in focus groups meeting towards the end of Stage 2.

Data collection

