The physiology data collection will be similar to stage 1; frequency and duration of data collection will be informed by the learning from the stage 1. The physiology data will be collected in the CRF and stored in the electronic databases. The questionnaire data including the responses from the EPDS, MIBS and paternal postnatal attachment scale will be stored in a REDCap database.

Data including the reasons parents did not want to consent for the study or cut short the cuddling episodes will be recorded.

The qualitative interviews will be audio-recorded, transcribed and anonymised.

Data Analysis

We will use descriptive statistics to report the parental questionnaire data and the adverse events. We will measure the mean or median (as appropriate) for the main physiological measures (see above). We will undertake three pairwise comparisons of pre-cuddle versus during-cuddle, during-cuddle versus post-cuddle and pre-cuddle versus post-cuddle using parametric t test or non-parametric Wilcoxon tests depending on the data distribution. We will derive the differences between the three

Date 11.02.2020 Version 1.6

23 of 37

IRAS No. 257430 CoolCuddle protocol

epochs (pre-cuddle, cuddle, and post-cuddle) and identify the magnitude of the differences, or variability which occurs. Using multilevel mixed-effects linear regression models, using data clustered by infant (or cuddle), we will assess if any difference in measures is likely to be due to chance (using a conventional level of statistical significance of p<0.05). We will also explore continuous monitoring of the physiological measures to establish variability over longer periods and the potential for adverse events. All data analysis will be conducted using the software SPSS or STATA.

We will compare our findings from the parental questionnaires with normative data. To compare parental bonding, we will collect these scores in our study to ensure they are in the satisfactory range following the "CoolCuddle". There are published normative data for mother-infant bonding scores³ and cut-offs for the father-infant attachment scores². We will compare our scores against these published data. We will also have detailed audit data on breastfeeding initiation and duration before September 2019 to compare with our study findings. If the cuddling process is stopped this will be treated as an adverse event and fully investigated to realise whether the problem is endemic, or modifiable and preventable.

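### Feeding at 8 weeks is a listed outcome, but neither the flow chart nor the data-collection text schedules it at the 8-week contact

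*Protocol*

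**What the plan says.** Protocol section 4.2 sets two times for the feeding outcome: "Mode and type of feeding at discharge and 8 weeks". It separately lists "Day of life when oral feeds established".

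Elsewhere feeding appears as follows:

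- **Study summary, Outcomes:** "attachment, mode of feeding at discharge and length of stay". No 8-week feeding item is given.
- **Flow chart, Stage 1:** "Mode & type of feeding; length of hospital stay" stands in the day 5-7 box. The later box, "Data at 8 weeks of life of baby", holds the EPDS and MIBS for mothers and the attachment scale for fathers.
- **Flow chart, Stage 2:** mode of feeding stands in the box before discharge. The box "When baby is 8 weeks old" holds the same three scales and parents' opinions of the cuddle.
- **Section 5.1, Data at discharge:** "We will collect data on mode and type of feeding", with no time point in the sentence itself.
- **Stage 2, Data collection:** "The questionnaire data including the responses from the EPDS, MIBS and paternal postnatal attachment scale will be stored in a REDCap database".

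The Stage 2 data analysis text plans to set the study's findings beside local audit data on the start and the duration of breastfeeding. The Stage 2 outcomes in the flow chart include a comparison of feeding mode with audit data.

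**The concern.** The outcomes section and the schedule disagree about what is collected at 8 weeks. An analysis plan cannot settle this later, because it concerns whether the data will exist at all.

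The 8-week item is the only listed quantitative outcome that reaches past discharge on feeding, so it is the one that could inform the duration half of the audit comparison. Section 9.6 also records that parents asked for breastfeeding to be among the outcomes. A feeding status that nobody asks about at 8 weeks is unlikely to be found afterwards in the neonatal unit's inpatient record.

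**Working it through.** No formula applies and the protocol gives no figure to reproduce. The check sets each feeding outcome in section 4.2 against every place that says what is collected and when.

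| Source | Feeding at or around discharge | Feeding at 8 weeks |
|---|---|---|
| 4.2 Outcomes | Listed | Listed |
| Study summary | Listed | Not listed |
| Flow chart, Stage 1 | Day 5-7 box | Not in the 8-week box |
| Flow chart, Stage 2 | Before-discharge box | Not in the 8-week box |
| 5.1, Data at discharge | Under this heading | Not stated; 8 weeks is attached to the maternal questionnaires |
| Stage 2, Data collection | Physiology as in Stage 1; feeding not mentioned | Three scales named, list open-ended |

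**Count.** Mode and type of feeding has 2 time points in 4.2. One (discharge) has a collection point and 1 (8 weeks) has none outside 4.2.

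**Consequence if the schedule is what gets built.** None of the 20-24 Stage 2 infants, and none of the 4-6 Stage 1 infants, would have an 8-week feeding value. This is conditional on forms following the flow chart and data-collection text. It is not a prediction.

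**Effect on the audit comparison.** It has two parts.

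1. Feeding mode at discharge: the data are scheduled, so this part stands.
2. Breastfeeding duration: this needs a feeding observation after discharge. The only one listed is the 8-week item, so this part has no scheduled data.

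**Day oral feeds are established.** This outcome appears in 4.2 and nowhere else. It probably falls during the hospital stay and could then be taken from the notes (an assumption; the protocol does not say). That makes it a form detail, separate from the 8-week gap.

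**The case against.** The strongest reply is that section 4.2 itself fixes the variable and its times, that an 8-week parent contact exists, and that nothing says feeding will not be asked there. Several parts of this reply are sound:

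- The flow chart is labelled a schematic and need not be a complete list.
- The discharge paragraph in 5.1 also covers questionnaires given at 8 weeks, so its heading does not strictly limit timing.
- The REDCap sentence is worded as an open list and concerns storage, so it does not exclude a feeding item.
- Section 8 describes parents' participation as limited to the three scales, but it does so to explain why adverse events are not recorded for parents. Parents also cuddle, talk aloud and are interviewed, so the sentence cannot be a closed list of data.
- The case report form and questionnaire pack are not shown and may already hold the item.
- Feeding is in none of the objectives in 4.1 and none of the traffic-light criteria in section 3.

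A reader might therefore be tempted to infer that the 8-week outcome is certain to be lost and the whole audit comparison with it. The documents support neither inference: the first depends on how the forms were built, and the discharge part of the comparison survives.

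What remains is that both 8-week boxes list their contents and omit feeding, while both stages place feeding at an earlier point and the summary names discharge only. These places agree with each other and differ from 4.2.

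**Conclusion.** The inconsistency is real and worth correcting. Feeding at 8 weeks is promised in 4.2 and scheduled nowhere else. If the schedule governs the forms, that outcome would be missing for all infants and the comparison of breastfeeding duration with audit data would have nothing behind it.

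That the loss would be permanent rests on the assumption that most infants are home by 8 weeks; the protocol gives no length of stay. Conclusions on safety and physiological stability are not affected.

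The day oral feeds are established might be read as a second lost outcome. It is better described as an item whose place of recording is unstated, since the inpatient notes probably hold it.

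**What to change.** Add mode and type of feeding to the existing 8-week questionnaire contact and to the database. Then align the study summary, both flow-chart stages, the data-collection text in section 5 and the description of parents' participation in section 8 with section 4.2. In the same edit, reconcile the Stage 1 day 5-7 placement of feeding with the discharge time point in 4.2.

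If the sponsor does not intend to collect feeding at 8 weeks, remove it from 4.2 and drop the breastfeeding-duration comparison.

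Optionally, record the date oral feeds were established on the discharge form, with a short definition of established.

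The cost is one or two extra questions for parents at a contact already planned, with minor changes to the forms and the protocol text.
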